## LIST OF ABBREVIATIONS

ABQoL	Autoimmune Bullous Disease Quality of Life
ADA	anti-drug antibodies
AE	adverse event
AECA	Anti-epithelial cell antibody
ALT	alanine aminotransferase
AST	aspartate aminotransferase
AUC 0-24	area under the serum concentration-time curve from pre-dose (time 0 ) to 24 hours post-dose
AUC 0-∞	area under the serum concentration-time curve from pre-dose (time 0 ) to infinity
BLQ	below the limit of quantification
BMI	body mass index
BUN	blood urea nitrogen
C1q	complement component 1q
C3	complement component 3
CAR-T	chimeric antigen receptor and T-cell
CFR	Code of Federal Regulations
CIC	circulating immune complexes
C max	maximum serum concentration determined directly from the concentration-time profile
CRO	contract research organization
CV	coefficient of variation
D5W	dextrose 5% in water
DEC	Dose Escalation Committee
DIF	direct immunofluorescence
DLT	dose-limiting toxicity
DNA	deoxyribonucleic acid
dsDNA	double-stranded deoxyribonucleic acid
Dsg	desmoglein
ECG	electrocardiogram
eCRF	electronic case report form
EDC	electronic data capture
eGFR	estimated glomerular filtration rate
ET	early termination
FCGR2A	Fc gamma R2a receptor
FcRn	neonatal Fc receptor
FDA	Food and Drug Administration
GCP	Good Clinical Practice
GLP	Good Laboratory Practice
H 2	histamine 2

HBV	hepatitis B virus
HCV	hepatitis C virus
HIPAA	Health Insurance Portability and Accountability Act
HIV	human immunodeficiency virus
HR-QoL	health-related quality of life
IB	Investigator's Brochure
IC	immune complex
ICF	Informed Consent Form
ICH	International Council for Harmonisation of Technical Requirements for Pharmaceuticals for Human Use
IgA	immunoglobulin A
IgG	immunoglobulin G
IgG1-4	immunoglobulin G1-G4
IgM	immunoglobulin M
IND	investigational new drug
IRB	institutional review board
IRR	infusion-related reaction
IUD	Intrauterine device
IV	intravenous
IVIG	intravenous immunoglobulin
LDH	lactate dehydrogenase
LLN	lower limit of normal
mAb	monoclonal antibody
MED	minimum effective dose
MedDRA	Medical Dictionary for Regulatory Activities
NCI CTCAE	National Cancer Institute Common Terminology Criteria for Adverse Events
NHP	nonhuman primate
NK	natural killer
NOAEL	no observed adverse effect level
PD	pharmacodynamics
PDAI	Pemphigus Disease Area Index
PK	pharmacokinetic
QTcF	corrected QT interval using Fridericia's formula
RNA	ribonucleic acid
RNAseq	RNA sequencing
SAE	serious adverse event
SAP	statistical analysis plan
SAS	Statistical Analysis System
SD	standard deviation
SNP	single nucleotide polymorphism
SOC	system organ class

SYNT001	a humanized, affinity matured IgG4-kappa monoclonal antibody
$t_{1/2}$	Half-life
TEAE	treatment-emergent adverse event
$T_{max}$	observed time to reach peak plasma concentration
ULN	upper limit of normal
US	United States of America
VZV	varicella zoster virus
WHO	World Health Organization
WHO-DD	World Health Organization Drug Dictionary

## 2. BACKGROUND AND RATIONALE

SYNT001, a humanized, affinity-matured IgG4-kappa monoclonal antibody (mAb), blocks immunoglobulin G (IgG) and IgG immune complex (IC) interactions with the neonatal crystallizable fragment receptor (FcRn), and inhibits the varied roles of FcRn in the immune response.

Through specific and high affinity blockade of FcRn, SYNT001 has been shown to increase the catabolism of IgG and IgG IC in healthy volunteers and is predicted to block the ability of IgG IC to activate intracellular signaling events associated with binding to FcRn. This predicts that SYNT001 will also accelerate degradation of endogenous circulating IgG autoantibodies and IgG-IC specifically involved in the pathogenesis of autoimmunity. Blocking FcRn interactions with IgG ICs further predicts that SYNT001 will have consequences for innate and adaptive cellular immunity. In the first instance, blocking multimeric IgG IC interactions with FcRn within antigen-presenting cells should result in inhibition of IC-mediated inflammatory cytokine production and release by these cells. In addition, as FcRn determines the intracellular itinerary of IgG ICs within and among compartments important in cellular immunity, it is further anticipated that SYNT001 will block antigen processing and presentation of antigens contained within ICs that would otherwise lead to CD8+ and CD4+ T cell activation. Thus, SYNT001 is expected to specifically target immune functions associated with IgG and IC that are involved in certain IgG-mediated autoimmune conditions.

SYNT001 targets key mechanisms contributing to pathology in a variety of IgG-mediated autoimmune disorders.

While current treatments for certain autoimmune disorders, including chronic steroids, immunosuppressants, intravenous immunoglobulin (IVIG), plasmapheresis, and anti-CD20 mAbs, such as rituximab, can be effective, they are associated with significant adverse effects, and delayed or non-durable responses.

Pemphigus is a rare group of blistering autoimmune diseases that affect the skin and mucous membranes. Autoantibodies are thought to play an important pathogenic role in the mucosal and cutaneous manifestations in patients with pemphigus. Administration of SYNT001 significantly decreases total IgG levels, including a corresponding decrease in the levels of the pathogenic autoantibodies. This may lead to a decrease in the mucosal and cutaneous manifestations in patients with pemphigus. Moreover, the ability of SYNT001 to reduce IgG ICs and the associated innate and adaptive immune responses may allow for further sustained disease modification.

### 2.1 Study Rationale

This study is being conducted to evaluate the safety, dose, pharmacokinetics (PK), pharmacodynamics (PD) and immunogenicity of intravenous (IV) SYNT001 as well as its effects on pemphigus disease activity markers.

## 2.2 Selection of Doses in this Study

The initial SYNT001 dose levels for study SYNT001-103 were selected following careful review of the safety, tolerability, and PD effect on total IgG levels studied in non-human primates (NHP) and healthy male subjects.

Four repeat-dose toxicology studies in cynomolgus monkeys examined 2 to 14 repeat weekly IV doses 5 to 100 mg/kg SYNT001 with up to a 4-week follow-up. There was one death in the 14-week study attributed to an immune-evoked infusion reaction, which correlated with the development of anti-drug antibodies (ADAs), circulating immune complexes, circulating complement depletion, and deposition of immune complexes containing SYNT001 and complement in tissues. Across studies, clinical signs were limited to reports of transient emesis/vomitus following dosing and facial flushing and periocular swelling observed in the 5-week study after the third dose coincident with the first appearance of ADAs. With the exception of emesis/vomitus, these clinical signs were effectively controlled with diphenhydramine pretreatment in the 5-week study and the subsequent 14-week study. There were no adverse SYNT001-related changes in weight gain, clinical chemistry, gross or histo-pathology. The No Observed Adverse Effect Level (NOAEL) was the highest dose tested in all 4 studies and the overall NOAEL following repeat weekly exposure to SYNT001 of up to 14 doses in cynomolgus monkeys was 100 mg/kg.

The safety, tolerability, and PD effect on total IgG levels in study SYNT-101—a Phase 1a study that assessed single ascending doses of SYNT001 in healthy male subjects—were also reviewed. In study SYNT-101, the doses of SYNT001 up to and including 30 mg/kg were well tolerated. There were no dose-limiting toxicities, serious adverse events (SAEs), or any other safety concerns. No adverse events (AEs) were observed in the 1 and 3 mg/kg dose cohorts. Headache was the most commonly reported treatment-emergent adverse event (TEAE), occurring in 8 of 11 subjects treated with 10 or 30 mg/kg SYNT001. One headache in the 10 mg/kg cohort was moderate (Grade 2) in severity; all other headaches were mild (Grade 1). One mild headache was treated with a single dose of acetaminophen; all other headaches resolved without treatment. Therefore, it is anticipated that the doses selected for this study should be well tolerated and have clinically relevant PD effects in patients with pemphigus.

Further consideration was given to the desired level of FcRn blockade to achieve suppression of IgG to a range that has been previously correlated with disease remission induced by immunoadsorption in autoimmune disorders such as pemphigus vulgaris and myasthenia gravis (ie, >50% decrease in total IgG from baseline) ([Blaha et al., 2011](#); [Eming and Hertl, 2006](#); [Kohler et al., 2011](#)).

The Sponsor also considered the potential effects of inhibiting FcRn function as they relate to IC associated innate and adaptive immunity. From the NHP studies, single doses of SYNT001 produced a dose-dependent decrease in total IgG and a further decrease was seen with repeated weekly doses up to a maximum of 70% reduction at 100 mg/kg. This magnitude of total IgG reduction is approaching the expected maximal 90% inhibition of FcRn function based on murine studies performed by the Sponsor and others ([Nixon et al., 2015](#); [Roopenian et al., 2003](#)). In the recently completed Phase 1a trial with SYNT001 in healthy volunteers a single dose caused a maximum average 50% drop in total IgG with IV dosing at 30 mg/kg. Based on the

NHP studies further reductions are expected following multiple dosing. A corresponding decrease in pathogenic autoantibodies is anticipated.

A semi-mechanistic model of FcRn-IgG interactions and FcRn inhibition with SYNT001 was jointly developed by Applied BioMath and the Sponsor. The model was designed to simulate PK and PD responses to various dosing regimens of SYNT001 to inform clinical trial design. Initial simulations were able to capture both PK and PD responses to single doses of SYNT001 from a single-ascending dose study in healthy volunteers and predict multiple dose responses from ongoing studies with good fidelity. The model predicted an IgG reduction of approximately 75% by Day 33, which was determined to be acceptably close to the actual mean IgG reduction of 59% by Day 30 observed in patients. Subsequent iterations of the model have used patient data from ongoing patient studies to further calibrate dose responses. In the most recent simulations, multiple dosing scenarios have been explored, including responses to weekly, bi-weekly, and loading doses. A simulated dosing regimen consisting of three weekly loading doses of 30 mg/kg SYNT001 followed by every other week maintenance doses of 10 mg/kg SYNT001 achieved a nadir IgG reduction of approximately 78% between Days 21 and 28 and maintained an IgG reduction between approximately 50% and 68%. This level of total IgG reduction has been associated with clinical efficacy in early studies of SYNT001-treated pemphigus subjects, and represents a target for future studies in other indications. This regimen of 30 mg/kg loading doses and 10 mg/kg maintenance doses was determined to be the optimal starting regimen to achieve meaningful IgG reduction while maximizing patient safety. Future cohorts may increase the maintenance doses to 20 mg/kg SYNT001, which the model predicts will achieve greater IgG reductions between approximately 55% and 72%. Given the rigorous biological approach taken in the development of the model, simulations of dosing schedules can be considered reliable for the purpose of planning clinical trials.

Several recently completed non-clinical studies support the proposed Cohort 2 dose and dosing regimen. A recently completed 27-week dose-response good laboratory practice (GLP) toxicology study in non-human primates assessed the long-term safety, toxicology, and toxicokinetics of weekly doses of SYNT001. Twenty-seven (27) once weekly 10-minute infusions of SYNT001, at doses of 5, 30, or 100 mg/kg, to cynomolgus monkeys was associated with non-adverse test article-related clinical effects and clinical pathology observations at  $\geq 5$  mg/kg. SYNT001 produced dose-dependent reduction of serum IgG levels without affecting IgA, IgM or albumin levels. The NOAEL of SYNT001 was 100 mg/kg following 17 infusions and 30 mg/kg following 27 infusions.

As indicated above, in the recently completed Phase 1a healthy male volunteer study, single doses of SYNT001 up to and including 30 mg/kg have been well tolerated. There were no dose limiting toxicities (DLTs), serious adverse events (SAEs), or any other safety concerns identified. No adverse events (AEs) were observed in the 1 and 3 mg/kg dose cohorts. The only moderate (Grade 2) AE observed was a single instance of headache in the 10 mg/kg cohort. Other subjects had mild (Grade 1) AEs at 10 mg/kg. In Cohort 4 (30 mg/kg), five subjects received SYNT001. All five subjects experienced AEs; all were mild (Grade 1), transient and resolved spontaneously without intervention. The most commonly reported AEs were headache.

A preliminary assessment of safety was conducted by SYNT001 Pemphigus Study SYNT001-103 Dose Escalation Committee (DEC). Seven subjects with pemphigus were treated with

10 mg/kg IV weekly doses over a period of 5 weeks. Overall, SYNT001 10 mg/kg IV was well tolerated. Headache (Grade 1 or 2, self-limited) was the only drug-related AE that was reported in more than one subject. Total IgG and CIC biomarkers were reduced by 59% and 50% respectively, from baseline levels following the fifth dose, returning to baseline within 1 to 2 months. Additionally, preliminary evidence of clinical efficacy as measured by a clinically validated scoring metric, the Pemphigus Disease Area Index, was observed across the population. The DEC approved a dose escalation of SYNT001 from 10 mg/kg IV weekly doses for 5 weeks to 30 mg/kg IV weekly doses for 5 weeks.

Given these preliminary data in non-clinical toxicology species and human subjects, as well as supporting evidence from the computational model, it is anticipated that the doses and dose regimens selected for this study will be well tolerated and will demonstrate clinically relevant pharmacodynamic effects and efficacy in patients with pemphigus. For a summary of findings from the single dose clinical study in healthy subjects and further details regarding the nonclinical findings, please refer to the SYNT001 Investigators Brochure.

### **2.3 Compliance Statement**

This study will be conducted in compliance with Good Clinical Practice (GCP), including the International Council for Harmonisation of Technical Requirements for Pharmaceuticals for Human Use (ICH) Guidelines and Food and Drug Administration (FDA) regulations, consistent with the principles outlined in the Declaration of Helsinki. In addition, the Investigator agrees to adhere to all applicable local laws and regulatory requirements relevant to the use of new therapeutic agents.

The study will be conducted in compliance with the protocol. The appropriate Institutional Review Boards (IRBs) must approve the protocol, any amendments, and the subject informed consent form (ICF) prior to implementation.

Freely given written informed consent must be obtained from every subject prior to participation in this clinical trial. As part of this procedure, the Investigator must explain orally and in writing the nature, duration, and purpose of the study, and the action of the drug in such a manner that the study subject is aware of the potential risks, inconveniences, or AEs that may occur. The study subject should be informed that he/she is free to withdraw from the study at any time. He/she will receive all information that is required by federal regulations and ICH guidelines. The Investigator or designee will provide the Sponsor with a copy of the IRB-approved informed consent form prior to the start of the study. The rights, safety, and well-being of participating subjects are the most important considerations and should prevail over interests of science and society.

Study personnel involved in conducting this trial will be qualified by education, training, and experience to perform their respective task(s). This trial will not use the services of study personnel where sanctions have been invoked or where there has been scientific misconduct or fraud (eg, loss of medical licensure, debarment).

### 3. STUDY OBJECTIVES AND ENDPOINTS

Primary Objectives	Primary Endpoints
Safety: To evaluate the safety of IV infusions of SYNT001 at different dose levels and dosing regimens in subjects with pemphigus (vulgaris or foliaceus)	Safety: The evaluation of SYNT001 safety based on vital signs, physical examinations, electrocardiograms (ECGs), clinical safety laboratory tests, the incidence of adverse events (AEs), treatment-emergent adverse events (TEAEs) and serious adverse events (SAEs) summarized by dose and dosing regimen, severity, and relationship to study drug
Dose Selection: To determine a MED of SYNT001 as assessed by (i) total IgG level nadir and (ii) the proportion of subjects that meet the criteria for response by Pemphigus Disease Area Index total activity score (PDAI)	Dose Selection: The determination of dose and dosing regimen of SYNT001 that achieves (i) total IgG level nadir decrease by $\geq 60\%$ and $\leq 90\%$ from baseline and (ii) a PDAI total activity score of $\geq 50\%$ reduction from baseline to allow further clinical development in subjects with pemphigus (vulgaris or foliaceus)
Secondary Objectives	Secondary Endpoints
To evaluate the efficacy of doses of SYNT001 at different dose levels and dosing regimens on pharmacodynamics (PD) biomarkers	The evaluation of PD biomarkers based on absolute serum levels and percent change from baseline of total IgG, IgG subtypes (IgG1-4), immunoglobulin A (IgA), immunoglobulin M (IgM), albumin, and CIC summarized by dose, dosing regimen and visit
To determine the pharmacokinetics (PK) of SYNT001 following IV infusions at different dose levels and dosing regimens	The determination of PK parameters including half-life ( $t_{1/2}$ ), maximum serum concentration determined directly from the concentration-time profile ( $C_{max}$ ), observed time of peak serum concentration ( $T_{max}$ ), area under the serum concentration-time curve from pre-dose (time 0 ) to 24 hours post-dose ( $AUC_{0-24}$ ), and area under the serum concentration-time curve from pre-dose (time 0 ) to infinity ( $AUC_{0-\infty}$ ), (Cohort 1); maximum serum concentration determined directly from the maximum serum concentration and corresponding $T_{max}$ (Cohort 2 onwards) summarized by dose, dosing regimen, visit and time point
To assess the efficacy of doses of SYNT001 at different dose levels and dosing regimens on disease markers	
 
The assessment of pemphigus disease activity by responses on the PDAI based on absolute and percent change from baseline, summarized by dose, dosing regimen and visit
 
The assessment of pemphigus disease activity by pathogenic antibody levels based on absolute and percent change from baseline of serum anti-desmoglein 1 and 3 antibody (anti-Dsg 1 and anti-Dsg
 

	3) levels summarized by dose, dosing regimen and visit
To measure the immunogenicity of SYNT001 administered at different dose levels and dosing regimens	The immunogenicity of SYNT001 as determined by presence of anti-SYNT001 binding antibodies and neutralizing antibodies summarized by dose, dosing regimen, visit and time point
Exploratory Objectives	Exploratory Endpoints
To explore the effect of SYNT001 at different dose levels and dosing regimens on biomarkers to understand the pathophysiology of the disease and the SYNT001 mechanisms of action	The exploration of SYNT001 mechanisms of action and effects of SYNT001 on pathophysiology summarized by dose, dosing regimen and visit as determined by: 
 
• Complement component 3 levels by nephelometry
 
• Anti-epithelial cell antibody (AECA) titers by indirect immunofluorescence
 
• Fc gamma R2A receptor (FCGR2A) single nucleotide polymorphisms (SNP) by genotyping
 
• Presence of disease and inflammatory markers by total RNA sequencing
 
• Immunophenotyping including measurements of T cells, monocytes, natural killer (NK) cells and B cells by flow cytometry
 
• Urine IgG levels to explore SYNT001 distribution and elimination (Cohort 1 only)
 
• Exploratory biomarkers to investigate immune response associated with pemphigus
 

To determine the impact of different SYNT001 dose levels and dosing regimens on the subject's use of corticosteroids to treat their pemphigus (vulgaris or foliaceus)	The evaluation of corticosteroid use during the study will be summarized by dose, dosing regimen and visit
To assess the impact of SYNT001 on the subject's health-related quality of life (HR-QoL) at different dose levels and dosing regimens	The assessment of SYNT001 impact on subject's health-related quality of life (HR-QoL) by responses to the Autoimmune Bullous Diseases Quality of Life (ABQoL) questionnaire and Skindex-29 scores summarized by dose, dosing regimen and visit
To assess the effect of SYNT001 on the appearance of skin and mucosal lesions at different dose levels and dosing regimens	The qualitative assessment of changes in appearance of skin and mucosal lesions as determined by photography presented by dose, dosing regimen and visit
To quantify the amount of SYNT001 in skin (skin biopsies optional)	The determination of SYNT001 levels in skin biopsies across timepoints (skin biopsies optional) (Cohort 1 only)

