**Table 4. Cohort Overview**

Cohort No.	No. of Subjects	SYNT001 Dose	No. of Doses	Frequency of Doses
1 a	Up to 8	10 mg/kg	5	Weekly
2 b	Up to 12	Loading: 30 mg/kg c	3 c	Weekly c
		Maintenance: 10 mg/kg c	5 c	Every other week c, d

- No more than 3 subjects with pemphigus foliaceus may be enrolled
- Two or fewer subjects with pemphigus foliaceus may be enrolled
- The dose, number of doses, and frequency of doses in Cohort 2 will be confirmed based on review of safety and PD evaluations, including but not limited to, dose-limiting toxicities, AEs, TEAEs, SAEs, and total IgG levels. Following Sponsor review of emerging safety, PD and efficacy data, the Loading dose may be reduced to 20 or 10 mg/kg weekly and/or the Maintenance dose may be increased to 20 or 30 mg/kg every other week and/or dose frequency may be increased to weekly.
- Ongoing safety and PD evaluations may result in modification of the dose and dosing regimen in Cohort 2. See APPENDIX 5 for the corresponding visit schedule.

Subjects will be enrolled at staggered intervals to facilitate adequate safety evaluation before dosing of subsequent subjects

At 24-hour and 7-day intervals described below, all available safety data (including but not limited to dose-limiting toxicities [DLTs], AEs, TEAEs, SAEs, and PD (including but not limited to IgG levels), will be reviewed.

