### **11.3 Sample Size Justification**

Formal sample size calculations were not performed. The number of subjects was chosen based on feasibility and was considered sufficient to meet the study objectives.

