#### **11.4.3.2 Dose Selection Data**

The evaluation of SYNT001 based on total IgG levels and responses on the PDAI total activity score from baseline will be summarized using descriptive statistics. Descriptive statistics will include mean, SD, coefficient of variation (CV), median, minimum, and maximum. The determination of dose and dosing duration of SYNT001 that achieves (i) total IgG level nadir decrease by  $\geq 60\%$  and  $\leq 90\%$  from baseline and (ii) a PDAI total activity score of  $\geq 50\%$  reduction from baseline to allow further clinical development in subject with pemphigus (vulgaris or foliaceus).

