##### **11.4.4.4 PDAI Data**

PDAI results will be summarized by score (total activity score, total damage score), cohort, and visit. Descriptive statistics will include absolute change from baseline, and percent change from

baseline. PDAI will also be summarized by disease severity category, mild (0 to 8), moderate (9 to 24), and severe ( $\geq 25$ ).

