#### **11.5 Interim Analysis**

No interim analysis is planned.

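### Two regimens that differ in dose, frequency and duration can show which of them meets the IgG and PDAI criteria, not a minimum effective dose; and Section 11 groups some results by cohort where Section 3 requires dosing regimen

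*Protocol*

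**What the plan says.** The dose-selection objective in protocol Section 3, repeated in the synopsis, is "To determine a MED of SYNT001 as assessed by (i) total IgG level nadir and (ii) the proportion of subjects" who meet the PDAI response criteria. The list of abbreviations gives MED as "minimum effective dose". The paired endpoint is "The determination of dose and dosing regimen of SYNT001 that achieves (i) total IgG level nadir decrease by" at least 60% and at most 90%, together with a fall of at least 50% in the PDAI total activity score. Section 11.3 reports no formal calculation and adds: "The number of subjects was chosen based on feasibility and was considered sufficient to meet the study objectives".

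Section 5.2 and Table 4 set out two open-label regimens. Cohort 1 (up to 8 subjects) receives 10 mg/kg weekly for 5 doses. Cohort 2 (up to 12) receives 30 mg/kg weekly for 3 doses, then 10 mg/kg every other week for 5 doses. Under footnote c to Table 4, after Sponsor review that includes emerging efficacy results, "the Loading dose may be reduced to 20 or 10 mg/kg weekly and/or the Maintenance dose may be increased to 20 or 30 mg/kg" at two-week intervals, and dosing may become weekly.

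On grouping, Section 3 attaches dose and dosing regimen to the safety, PDAI and immunogenicity endpoints. Section 11.4.2 uses dose level and cohort. Section 11.4.3.2, on dose selection, names no grouping: "Descriptive statistics will include mean, SD, coefficient of variation (CV), median, minimum, and maximum". Section 11.4.4.4 says: "PDAI results will be summarized by score (total activity score, total damage score), cohort, and visit". Section 11.4.4.3 (immunogenicity) and the vital-sign and QTcF displays in Section 11.4.3.1 also use cohort.

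**The concern.** To call a regimen the minimum effective one, a trial must test something lower and see it fall short, and must be able to say which feature of the regimen was lowered. Here nothing below Cohort 1 is given, and the step from Cohort 1 to Cohort 2 changes several features at once. As worded, the objective invites a conclusion that the data cannot support, and Section 11.3 calls the sample size sufficient for it.

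The grouping matters because Cohort 2 is not fixed. If its regimen changes during enrolment, a by-cohort PDAI summary would average over subjects treated differently. PDAI response is one of the two criteria on which the dose is to be selected.

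**Working it through.** **Planned size.** 8 + 12 = 20, which agrees with the stated maximum of 20. The protocol gives no power, effect size or response rate, so there is no design figure to reproduce.

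**Ordering of the starting regimens** (Section 5.2; dosing days from Tables 2 and 3). Cumulative dose in mg/kg:

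| Day | 0 | 7 | 14 | 21 | 28 | Total |
|---|---|---|---|---|---|---|
| Cohort 1 | 10 | 20 | 30 | 40 | 50 | 5 × 10 = 50 |
| Cohort 2 | 30 | 60 | 90 | 90 | 100 | 3 × 30 + 5 × 10 = 140 |

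- Peak dose: 30 vs 10 mg/kg, so Cohort 2 is higher.
- Cumulative dose: Cohort 2 is higher on every Cohort 1 dosing day and in total.
- Maintenance rate: 10/2 = 5 mg/kg/week in Cohort 2 vs 10 mg/kg/week in Cohort 1, so Cohort 2 is lower.
- Average rate: 140/14 to 140/13 = 10.0 to 10.8 mg/kg/week in Cohort 2 vs 50/5 = 10.0 in Cohort 1, so about equal. The range depends on whether the last dose is counted as covering one week or two.
- Treatment period (Section 5.4): 84 vs 28 days.

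The regimens are therefore ordered on peak and cumulative dose, but not on every measure of dose.

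**What each outcome would show.**

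- Cohort 1 meets the criteria, with or without Cohort 2: nothing lower was tested, so Cohort 1 is not shown to be the minimum.
- Only Cohort 2 meets them: the loading doses, the longer treatment and the larger total cannot be separated, so what is needed for effect is not identified.
- Neither meets them: there is no effective regimen to call minimum.

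These outcomes are realistic. Section 2.2 reports a mean IgG reduction of 59% after the fifth dose in seven Cohort 1 subjects, beside the 60% bound, and a modelled nadir of about 78% for the Cohort 2 regimen. The 59% is a mean at one time, not a count of subjects whose own nadir reached 60%.

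**Scope for change in Cohort 2** (footnote c). Loading 30, 20 or 10; maintenance 10, 20 or 30; every other week or weekly: 3 × 3 × 2 = 18 combinations. This is a ceiling, not a plan. Three of them (loading at 10, maintenance every other week at 10, 20 or 30) fall below Cohort 1's cumulative dose on Day 21, in one case through Day 35, and exceed it later, so even that order can cross.

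**Grouping, side by side.**

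| Outcome | Section 3 | Section 11 |
|---|---|---|
| PDAI | dose, regimen, visit | cohort, visit (11.4.4.4) |
| Immunogenicity | dose, regimen, visit, time point | cohort, visit, time point (11.4.4.3) |
| Vital signs | dose and regimen | cohort (11.4.3.1) |
| ECG, for QTcF | dose and regimen | cohort (11.4.3.1) |
| Dose selection | dose and regimen that meets the criteria | none stated (11.4.3.2) |

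The synopsis statistics repeat the by-cohort wording for PDAI and immunogenicity.

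**Precision.** At a hypothetical response of one half, exact (Clopper-Pearson) 95% intervals are 16% to 84% for 4/8, 21% to 79% for 6/12, 12% to 88% for 3/6 and 7% to 93% for 2/4. The last two show the effect of splitting Cohort 2 into smaller regimen groups.

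**The case against.** The strongest reply is that MED is only a label. The paired endpoint already asks which dose and regimen reaches the two targets, so that further development can proceed, and MED can be read as the lowest tested regimen that does so. That reading is reasonable for a Phase 1b/2 study. It is also close to the wording proposed below, but it is not what the objective and the abbreviation list say.

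Several stronger readings are tempting, and the documents do not support them.

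- A reader might infer that the two regimens cannot be ordered by dose at all. The starting regimens can be, on peak and cumulative dose; the order fails on maintenance rate.
- A reader might infer that all results are pooled by cohort. The synopsis groups the dose-finding analysis by dose and dose regimen. Section 11.4.2 uses dose level as well as cohort and requires displays to account for differences between planned and received treatment. No text orders pooling. What stands is an inconsistency in named displays.
- A reader might infer that footnote c contradicts Section 11.5 ("No interim analysis is planned"). The review is disclosed, the study is open-label, and Section 11 is descriptive with no hypothesis test, so ongoing data review need not be a formal interim analysis.
- A reader might infer that the responder proportion has been dropped, because Section 11.4.3.2 lists only statistics for continuous data. Section 11.4.2 provides frequencies and percentages for categorical data, so it is not excluded.
- A reader might fault the power to compare the cohorts. The protocol plans no such comparison.

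**Conclusion.** The point stands in a limited form. The trial can show whether each tested regimen meets the IgG and PDAI criteria. It cannot show that any of them is the minimum effective dose, because no regimen below Cohort 1 is given, dose, frequency and duration change together, and Cohort 2 may itself change. This follows from the stated design and needs no assumed response rate; the intervals above only indicate scale.

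Separately, Sections 11.4.3.1, 11.4.4.3 and 11.4.4.4 conflict with Section 3 on grouping. The conflict has practical effect only if Cohort 2's regimen changes; if it does not, cohort and regimen coincide. This should be corrected, but it does not invalidate the trial and implies nothing about which dose is right.

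**What to change.** 1. In the synopsis (rationale and objectives) and Section 3, replace the aim of determining a MED with assessing which tested regimens meet the IgG and PDAI criteria. Limit the sufficiency statement in Section 11.3 to that aim.
2. In Sections 11.4.3.1 (vital signs, QTcF), 11.4.4.3 and 11.4.4.4, and in the matching synopsis text, change the grouping from cohort to dosing regimen received.
3. State the same grouping in Section 11.4.3.2, and report there the number and proportion of subjects meeting the criteria, with an exact 95% CI, for each regimen received. The rule for a subject whose regimen changes during treatment can be left to the SAP.
4. Optionally, add to Section 11.5 a cross-reference to the review described in footnote c.

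The cost is a protocol wording change and revised table shells, with no added subjects or procedures. The claim becomes more modest, and if Cohort 2 changes the per-regimen groups will be small and their intervals wide.
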